#### **6 REGULATORY ASPECTS AND SAFETY**

#### 6.1 Local regulations / Declaration of Helsinki

This study is conducted in compliance with the protocol, the current version of the Declaration of Helsinki, the ICH-GCP (ClinO Art. 5, Abs 2), the HRA as well as other locally relevant legal and regulatory requirements.

#### 6.2 (Serious) Adverse Events and notification of safety and protective measures

An Adverse Event (AE) is any untoward medical occurrence in a patient or a clinical investigation participant which does not necessarily have a causal relationship with the trial procedure. An AE can therefore be any unfavourable or unintended finding, symptom, or disease temporally associated with a trial procedure, whether or not related to it.

A Serious Adverse Event (SAE) (ClinO, Art. 63) is any untoward medical occurrence that

- Results in death or is life-threatening,
- Requires in-patient hospitalisation or prolongation of existing hospitalisation,
- Results in persistent or significant disability or incapacity, or
- Causes a congenital anomaly or birth defect

Both Investigator and Sponsor make a causality assessment of the event to the trial intervention, (see table below based on the terms given in ICH E2A guidelines). Any event assessed as possibly, probably or definitely related is classified as related to the trial intervention.

Relationship	Description		
Definitely	Temporal relationship		
	Improvement after dechallenge*		
	Recurrence after rechallenge		
	(or other proof of drug cause)		
Probably	Temporal relationship		
	Improvement after dechallenge		
	No other cause evident		
Possibly	Temporal relationship		
	Other cause possible		
Unlikely	Any assessable reaction that does not fulfil the above conditions		
Not related	Causal relationship can be ruled out		
*Improvement after dechallenge only taken into consideration, if applicable to reaction			

Both Investigator and Sponsor make a severity assessment of the event as mild, moderate or severe. Mild means the complication is tolerable, moderate means it interferes with daily activities and severe means it renders daily activities impossible.

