The present project proposes a mixed-method study to test the feasibility and acceptability of cultural prescription for patients with lifestyle-related pathological conditions. Additionally, it aims to explore whether there is any indication of improvement in health orientation and health outcomes as a result of the intervention.

According to ClinO, Art. 61, this study falls under Risk Category A (minimal risk). The rationale for this categorization stems from the fact that the study involves procedures that are well-established in research (blood draw, urine test, medical examination, smartwatch monitoring, and completing questionnaires), which are common and have minimal risks. These risks are primarily associated with the physical examination and the blood draw, which are generally safe procedures, and the potential for discomfort or mild anxiety. Additionally, the cultural prescribing intervention (art workshops, cultural activities) poses no more than minimal psychological or physical risk, given the nature of the activities involved.

Regarding the relevance of "sex and gender" dimensions, these factors are indeed pertinent to the study. Sex and gender influence health outcomes and can affect how individuals experience and engage with health interventions. Biological differences (e.g., hormone levels, genetics) and social constructs (e.g., gender roles, expectations) may impact participants' responses to cultural prescribing activities, particularly in the context of older adults with lifestyle-related conditions. Therefore, gender dimensions will be taken into account to ensure that interventions are equitable and tailored to the needs of different participants. This will include analyzing any potential differences in engagement with and outcomes from the cultural prescribing intervention based on gender.

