#### Reporting of SAEs (see ClinO, Art. 63)

All SAEs are documented and reported immediately (within a maximum of 24 hours) to the Sponsor of the study.

If it cannot be excluded that the SAE occurring in Switzerland is attributable to the intervention under investigation, the Investigator reports it to the Ethics Committee via BASEC within 15 days.

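### Section 6.2 judges causality only against the intervention and on a drug scale, so harm from study procedures is recorded but never attributed to them

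*Protocol*

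**What the plan says.** Section 6.2 of the Protocol ties the definition of an adverse event to a trial procedure. The causality judgement that follows has a different object: "Both Investigator and Sponsor make a causality assessment of the event to the trial intervention". It is made on a five-grade table, with this rule for the top three grades: "Any event assessed as possibly, probably or definitely related is classified as related to the trial intervention".

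The table's criteria are:

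- *Definitely*: timing, improvement after dechallenge, and recurrence after rechallenge, with "or other proof of drug cause" as the alternative.
- *Probably*: timing, improvement after dechallenge, and no other evident cause.
- *Possibly*: timing, plus "Other cause possible".
- *Unlikely*: "Any assessable reaction that does not fulfil the above conditions".
- *Not related*: "Causal relationship can be ruled out".

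A footnote says that dechallenge counts only where it is applicable.

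Every SAE goes to the Sponsor within 24 hours. The 15-day report to the Ethics Committee is required when it cannot be excluded that the SAE is "attributable to the intervention under investigation". The annual list in section 6.3 also gives causality to the intervention only. On where harm is expected, section 2 says: "These risks are primarily associated with the physical examination and the blood draw". The ethical considerations in the synopsis say much the same and add the smartwatch.

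**The concern.** The attribution question does not cover the procedures that the protocol itself names as its main source of risk. If a participant faints and is injured at a blood draw, the form asks whether the course caused it. The answer is no, and there is no place to record that a study procedure did. The written Ethics Committee trigger is not met either.

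The grading table was also built for a drug that can be stopped and restarted. Applied to dance, theatre or painting sessions, its top grade has criteria that an activity cannot meet. Its lowest related grade asks only for timing and another possible cause, in a population selected for chronic illness.

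At stake are which SAEs reach the Ethics Committee within 15 days, and whether the pilot can tell the planned RCT what harm came from the activity, from the research procedures, or from background illness.

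**Working it through.** The protocol gives no event figure to reproduce. The check sets its statements side by side and then reads the table as a decision rule.

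**1. What each safety element is judged against**

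| Element | Place | Object |
|---|---|---|
| AE definition | 6.2 | trial procedure |
| Severity grade | 6.2 | the event, whatever its cause |
| SAE report to Sponsor, 24 hours | 6.2, Reporting of SAEs | all SAEs |
| Causality grade | 6.2 | intervention only |
| Ethics Committee report, 15 days | 6.2, Reporting of SAEs | intervention only |
| Annual causality list | 6.3 | intervention only |
| Main risks named | 2; synopsis | examination and blood draw (synopsis adds smartwatch) |

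The last row does not match the three rows above it.

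**2. Could the intervention be read to include the procedures?** Section 3.4 describes it as the link worker and the activities. Section 2 gives the procedures and the cultural intervention separate risk statements. Appendix 1 has separate rows for the blood draw and the intervention. The text does not support the wider reading.

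**3. A serious event caused by the baseline blood draw.** Under section 4.3 the link worker makes contact about 3–4 weeks after baseline. An event at that draw precedes the intervention, so it has no temporal relationship to it and falls under *Unlikely* or *Not related*. The Ethics Committee trigger does not apply. At the 6-month visit, close to the end of the course, an uncertain assessor could choose *Possibly*, but that attributes the event to the course. An assessor sure that the draw was the cause would again find no trigger.

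Exposure to such events: 100 participants × 3 assessments = 300 planned visits. Section 3.2 waives the baseline tests where the GP has done them in the preceding month, so planned blood draws number between 100 × 2 = 200 and 100 × 3 = 300. These are counts of procedures, not of events. The protocol gives no rate of serious procedure events.

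**4. The table as a decision rule**

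- *Definitely* needs recurrence on rechallenge or proof of a drug cause. The footnote waives only dechallenge. Even a witnessed injury caused by an exercise in class does not literally qualify.
- *Probably* remains reachable. For a one-off injury dechallenge is not applicable, which leaves timing and no other evident cause.
- *Possibly* needs timing, which is undefined, and another possible cause. Section 3.4 plans weekly sessions, so with attendance as planned any event during the course lies within 7 days of a session. Section 4.1 requires at least one chronic condition, which readily supplies the other cause. A COPD exacerbation in month 3 therefore fits *Possibly* as written and counts as related unless the assessor rules causation out.
- *Unlikely* takes only what fails the rows above, so it gives little room for such an admission. The table does not say which row prevails when an event fits both *Possibly* and *Not related*.

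**5. How many admissions could be affected.** The documents give no admission rate. Assume 10–30% a year:

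- Low: 80 × 0.5 year × 0.10 = 4
- High: 80 × 0.5 year × 0.30 = 12

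These are background admissions during the course. They equal misclassified events only if none is ruled *Not related*.

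**The case against.** Several stronger readings are tempting, and the documents do not support them.

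- *Procedure events are lost.* They are not. They are adverse events by definition, are graded for severity, and if serious reach the Sponsor within 24 hours. Immediate safety measures go to the Ethics Committee within 7 days, and a list of safety events goes to it every year. Only the attribution and the 15-day trigger are missing.
- *A fall in class gets the same grade as an unrelated admission.* In the ordinary case it does not. The dechallenge footnote lets a fall with no other evident cause reach *Probably*, which already counts as related. The two grades coincide only when another cause is also in play.
- *Almost any admission during the course will be classed as related.* This is an inference. *Not related* stays open to the assessors, and nothing says that any event within the six months satisfies the timing criterion.
- *The minimal-risk claim can be neither supported nor refuted.* This does not follow, since events and their severity are recorded. Safety is not among the stated objectives or endpoints, and an over-inclusive grade leads to more reporting, not less.

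It can also be said that the protocol ties the Ethics Committee trigger to ClinO Art. 63, which is not at hand. That stands, and it is a reason not to propose narrowing the trigger.

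None of this removes the mismatch between the object of the AE definition and the object of the causality judgement, or the drug wording in a trial without a drug.

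**Conclusion.** The point holds in a limited form. Section 6.2 defines events by procedure and attributes them by intervention, although the protocol names the blood draw and the examination as its main risks. A serious event caused by a procedure is captured, but it is not attributed to the procedure and does not meet the written Ethics Committee trigger. This is clearest for the baseline draw, and it rests on the text alone.

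On the scale, *Definitely* is practically unreachable, and *Possibly* can take in background admissions unless causation is ruled out. The figure of 4–12 is an upper bound that depends on the assumed 10–30% annual admission rate and on *Not related* never being used. The practical consequence is blurred safety attribution in a pilot meant to prepare an RCT. The feasibility outcomes are not affected.

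**What to change.** Reconcile section 6.2, the SAE reporting paragraph and section 6.3 as follows:

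- Record causality twice for each event: (a) to the activity and link-worker contact, and (b) to study procedures, meaning the blood draw, examination and device.
- Report to the Ethics Committee any SAE for which attribution to (a) or (b) cannot be excluded, and carry both attributions into the annual list. Leave the existing exclusion test as wide as it is, and check the extended wording against ClinO Art. 63.
- Replace rechallenge and proof of a drug cause with terms that fit an activity, for example whether the event arose during or directly from a session or procedure.
- State what counts as a temporal relationship, and add plausibility of mechanism as a graded item. Use it to describe the strength of attribution, not to narrow the reporting trigger.
- Say which row prevails when an event fits more than one.

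The cost is a rewording of these sections and one extra field on the adverse event form. The downside is that procedure-related SAEs become reportable to the Ethics Committee.

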#### Reporting of SAEs (see ClinO, Art. 63)

All SAEs are documented and reported immediately (within a maximum of 24 hours) to the Sponsor of the study.

If it cannot be excluded that the SAE occurring in Switzerland is attributable to the intervention under investigation, the Investigator reports it to the Ethics Committee via BASEC within 15 days.

#### Follow up of (Serious) Adverse Events

Participants who terminate the study with ongoing (Serious) Adverse Events (SAEs) will be asked to participate in a final assessment.

#### Notification of safety and protective measures (see ClinO, Art 62, b)

If immediate safety and protective measures have to be taken during the conduct of the study, the investigator notifies the Ethics committee of these measures, and of the circumstances necessitating them, within 7 days.

#### 6.3 Periodic reporting of safety and general progress of the clinical trial.

Once a year, the investigator submits to the Ethics Committee a list of the safety events including the severity of the events, their causality to the intervention and the safety of the study participants. The investigator also informs the Ethics Committee about the general progress of the clinical trial (ClinO, Art. 43).

#### **6.4 Amendments**

Substantial changes to the study setup and study organization, the protocol and relevant study documents are submitted to the Ethics Committee for approval before implementation. Under emergency circumstances, deviations from the protocol to protect the rights, safety and well-being

of participants may proceed without prior approval of the Ethics Committee. Such deviations shall be documented and reported to the Ethics Committee as soon as possible. A list of all non-substantial amendments will be submitted once a year to the competent EC together with the safety report / general study progress report.

# 6.5 Notification and reporting upon completion, discontinuation or interruption of the study

Upon regular study completion, the Ethics Committee is notified via BASEC within 30 days (ClinO, Art. 38). The last follow-up visit of the last study participant is defined as the end of the trial. The Sponsor may terminate the study prematurely according to certain circumstances, e.g.

- Ethical concerns,
- Insufficient participant recruitment,
- When the safety of the participants is doubtful or at risk (e.g. when the benefit-risk assessment is no longer positive),
- Early evidence of harm or benefit of the experimental intervention

Upon premature study termination or study interruption, the Ethics Committee is notified via BASEC within 15 days (Article 38 ClinO).

All biological materials and health-related data are anonymised upon end of data analysis.

A final report is submitted to the Ethics Committee via BASEC within a year after completion or discontinuation of the study (ClinO, Art. 38).

#### 6.6 Insurance

In the event of study-related damage or injuries, the liability of the Ente Ospedaliero Cantonale provides compensation, except for claims that arise from misconduct or gross negligence.

#### 7 FURTHER ASPECTS

#### 7.1 Overall ethical considerations

The study will be conducted in accordance with **ethical guidelines**, with approval sought from the Ethics Committee of the Canton of Ticino. Participants' confidentiality and rights will be protected throughout the study.

Data will be systematically uploaded for analysis to **SwitchDrive**, a secure data storage system. Participants will each be assigned a unique identifier, and quantitative data from the questionnaires will be entered into an **Excel spreadsheet** by a designated researcher and subsequently checked for accuracy by a second researcher.

Informed consent will be obtained in writing before participation, ensuring that participants understand their right to withdraw from the study at any time without any consequences to their medical care. To minimize potential biases and preserve the integrity of the data, participants will not be informed in advance whether they are assigned to the experimental or control group. Instead, they will be provided with a general explanation of the study's objectives and the existence of two groups with different activities, without specifying the nature of each group's participation. At the conclusion of the second follow-up, participants will be fully debriefed about the study design and group allocation. This approach is in line with Article 18 of the Federal Act on Research involving Human Beings. Participants will receive an appropriate debriefing both

orally and in written form, and will be asked to provide written informed consent to the use of their data.

The **well-being of participants** will be the primary concern throughout the study. Any adverse effects or unintended consequences arising from participation in the event will be monitored and addressed promptly. Participants will be provided with support resources if needed, especially if their involvement leads to unexpected emotional or psychological responses.

To ensure a **safe and supportive environment**, link workers and staff involved in the study will be adequately trained to recognize and respond to participants' needs, including managing any emotional or psychological challenges that may arise during the activities. This training will equip them to provide appropriate guidance and support, ensuring that participants feel comfortable and secure throughout their involvement in the project. If a participant requires immediate attention, link workers will promptly get in contact with the participant's GP to ensure that appropriate medical or psychological support is provided.

The recruitment process will ensure that all eligible individuals have an **equal opportunity** to participate, without discrimination based on race, gender, socioeconomic status, or other factors. Efforts will be made to accommodate participants with diverse needs, ensuring that the cultural prescriptions are accessible and inclusive.

#### 7.2 Risk-benefit assessment

The study carries minimal risks, including discomfort from blood draws, monitoring device wear, or participation in cultural activities. However, we expect immediate benefits from the artistic or cultural activities, which may enhance participants' well-being and health outcomes. Risks of unauthorized data access are mitigated by using anonymized data, secure storage with password protection, and limited access to research team members. While the primary goal is to assess the feasibility and preliminary impact of cultural interventions, the study also offers participants the opportunity to engage in activities that may improve their health and quality of life, with results contributing to future healthcare practices.

#### 8 QUALITY CONTROL AND DATA PROTECTION

#### 8.1 Quality measures

To ensure quality assurance and control, several measures will be implemented throughout the study. Data entry will be regularly reviewed by a second person to ensure accuracy and consistency. All study personnel will undergo training on key aspects of the study, including ethical considerations, participant management, and proper handling of data and biological material. Additionally, regular team meetings will be held to address any issues and ensure ongoing quality management. For quality assurance the sponsor, the Ethics Committee or an independent trial monitor may visit the research sites. Direct access to the source data and all study related files is granted on such occasions. All involved parties keep the participant data strictly confidential.

#### 8.2 Data recording and source data

Study data will be recorded using an electronic Case Report Form (eCRF) in secuTrial®, ensuring secure and standardized data collection. An **audit trail** will be maintained to track all data entries and modifications. Each participant will have an individual **eCRF**, which will not contain identifiable information such as names or birth dates but will instead use a **unique coded identifier**. This coding system ensures participant confidentiality while allowing data linkage for analysis. Access

to the eCRF will be restricted to authorized study personnel only, with role-based permissions to prevent unauthorized modifications or access.

The study will collect source data through study-specific questionnaires (administered on a tablet), laboratory test results from blood draws conducted specifically for the study, medical examinations performed as part of study assessments, and data from a wearable device. Additionally, routinely collected data, including baseline laboratory test results from the past three months and relevant pre-existing medical history or medication records, will be imported into the electronic Case Report Form (eCRF).

#### 8.3 Confidentiality and coding

The investigator affirms and upholds the principle of the participant's right to privacy and that they shall comply with applicable privacy laws. Especially, anonymity of the participants shall be guaranteed when presenting the data at scientific meetings or publishing them in scientific journals.

The investigator has appropriate knowledge and skills in the areas of data security and data protection or is able to ensure compliance by calling in appropriate expertise (Art. 6, ClinO). Individual subject medical information obtained as a result of this study is considered confidential and disclosure to third parties is prohibited.

Trial and participant data will be handled with the utmost discretion and is only accessible to authorised personnel who require the data to fulfil their duties within the scope of the study. On the CRFs and other study specific documents, participants are only identified by a unique participant number.

The participant identification list will be securely stored by the research team at the University on SwitchDrive, a secure cloud storage service. Access to the list will be strictly limited to authorized research personnel, protected by password authentication and two-factor verification. To prevent unauthorized or accidental disclosure, alteration, deletion, copying, or theft, data will be regularly backed up on encrypted storage media. An audit trail, in accordance with ClinO, Art. 18, will ensure traceability by maintaining a record of all data modifications and access logs.

Biological material in this study is not identified by participant name but by a unique participant number. Biological material is appropriately stored in a restricted area only accessible to the authorised personnel. Traceability is ensured through a digital tracking system that records sample collection, storage, and any subsequent handling. The biological material is preserved in temperature-controlled freezers with continuous monitoring and alarm systems to detect temperature fluctuations. Regular maintenance and calibration of cooling equipment are conducted to ensure optimal storage conditions, preventing sample degradation and maintaining the integrity of the biological material.

